2.3. Definitions of Patient Demographic Factors and Indicators of Treatment Status

No	Patient demographic factor	Description
1	Sex	Male, female, unknown/unspecified
2	Pregnancy status	Not pregnant, currently pregnant, unknown/unspecified
3	Breastfeeding status	Not breastfeeding, currently breastfeeding, unknown/unspecified
4	Age category-1	<15 years old, ≥15 years old, unknown/unspecified
5	Age category-2	<6 years old, ≥6 years old and <12 years old, ≥12 years old and <18 years old, ≥18 years old, unknown/unspecified
6	Age	Actual value
7	Body height category-1	<140 cm, ≥140 cm and <150 cm, ≥150 cm and <160 cm, ≥160 cm and <170 cm, ≥170 cm and <180 cm, ≥180 cm, unknown/unspecified
8	Body height	Actual value
9	Body weight category-1	<30 kg, ≥30 kg and <40 kg, ≥40 kg and <50 kg, ≥50 kg and <60 kg, ≥60 kg and <70 kg, ≥70 kg and <80 kg, ≥80 kg, unknown/unspecified
10	Body weight	Actual value
11	BMI category-1	<18.5, ≥18.5 and <25, ≥25, unknown/unspecified
12	BMI	Actual value Body weight / (Body height/100)**2 The value will be indicated to two decimal places rounded from three decimals.
13	Inpatient/outpatient category	Inpatient, outpatient, unknown/unspecified
14	Presence or absence of concurrent diseases	Absent, present, unknown/unspecified
15	Presence or absence of concurrent hepatic impairment	Absent, present, unknown/unspecified
16	Presence or absence of concurrent renal impairment	Absent, present, unknown/unspecified
17	Presence or absence of concurrent respiratory disease	Absent, present, unknown/unspecified
18	Presence or absence of other concurrent diseases	Absent, present, unknown/unspecified
19	Presence or absence of previous diseases	Absent, present, unknown/unspecified
20	Presence or absence of allergy history	Absent, present, unknown/unspecified
21	Presence or absence of previous drugs	Absent, present, unknown/unspecified
22	Presence or absence of concomitant digestive enzyme preparations	Absent, present, unknown/unspecified
No	Indicator of treatment status	Description
23	Dosage form	Granule, capsule, granule + capsule, unknown/unspecified

No	Patient demographic factor	Description
24	Duration of treatment (safety) (excluding any rest period)	≤28 days, >28 days and ≤56 days, >56 days and ≤84 days, >84 days and ≤168 days, >168 days and ≤252 days, >252 days and ≤336 days, >336 days and ≤364 days, >364 days and ≤2 years, >2 years and ≤3 years, >3 years and ≤4 years, >4 years and ≤5 years, >5 years and ≤6 years, >6 years and ≤7 years, unknown/unspecified In the summarization for the occurrence status of adverse events and adverse drug reactions, the duration of treatment in a patient experiencing an adverse event or adverse drug reaction will be determined based on the number of days until the initial onset date of the event (including the date of onset).
25	Duration of treatment (effectiveness rate) (excluding any rest period)	≤28 days, >28 days and ≤56 days, >56 days and ≤84 days, >84 days and ≤168 days, >168 days and ≤252 days, >252 days and ≤336 days, >336 days and ≤364 days, unknown/unspecified
26	Duration of treatment (safety) (excluding any rest period)	Actual value
27	Duration of treatment (effectiveness rate) (excluding any rest period)	Actual value until Day 364 excluding any rest periods
28	Total dose (safety)	Categories will be determined based on the distribution of actual data.
No	Indicator of treatment status	Description
29	Total dose (effectiveness rate)	Categories will be determined based on the distribution of actual data.
30	Total dose (safety)	Actual value of the total dose during the duration of use of Lipacreen (safety)
31	Total dose (effectiveness rate)	Actual value of the total dose during the duration of use of Lipacreen (effectiveness rate)
32	Reason for dose change (safety) (multiple answers are allowed)	Reason for dose change during the duration of use of Lipacreen (safety) Unsatisfactory therapeutic effect, occurrence of an adverse event, patient's request, other
33	Reason for dose change (effectiveness rate) (multiple answers are allowed)	Reason for dose change during the duration of use of Lipacreen (effectiveness rate) Unsatisfactory therapeutic effect, occurrence of an adverse event, patient's request, other
34	Treatment compliance (safety) (multiple answers are allowed)	Treatment compliance during the duration of use of Lipacreen (safety) Good, half, poor, unknown/unspecified
35	Treatment compliance (effectiveness rate) (multiple answers are allowed)	Treatment compliance during the duration of use of Lipacreen (effectiveness rate) Good, half, poor, unknown/unspecified
36	Initial daily dose (mg/day)	The initial daily dose will be determined based on the daily dose on the start date of treatment with Lipacreen. <900, 900, >900 and <1800, 1800, >1800, unknown/unspecified

No	Patient demographic factor	Description
37	Mean daily dose (safety) (mg/day)	
The mean daily dose will be determined based on the mean daily dose (safety). <900, 900, >900 and <1800, 1800, >1800, unknown/unspecified
 
The mean daily dose for each dose observation period will be determined based on the mean daily doses during the individual periods shown below.
 
Dose observation periods:
 
 At the start of treatment: Day 1 At Week 2: Day 2 to Day 14 At Week 4: Day 15 to Day 28 At Week 8: Day 29 to Day 56 At Week 16: Day 57 to Day 112 At Week 24: Day 113 to Day 168 At Week 32: Day 169 to Day 224 At Week 40: Day 225 to Day 280 At Week 48: Day 281 to Day 336 At Week 52: Day 337 to Day 364 At Year 2: Day 365 to Day 728 At Year 3: Day 729 to Day 1092 At Year 4: Day 1093 to Day 1456 At Year 5: Day 1457 to Day 1820 At Year 6: Day 1821 to Day 2184 At Year 7: Day 2185 to Day 2400

No	Indicator of treatment status	Description
38	Mean daily dose (effectiveness rate) (mg/day)	
The mean daily dose will be determined based on the mean daily dose (effectiveness rate). <900, 900, >900 and <1800, 1800, >1800, unknown/unspecified
 
The mean daily dose for each dose observation period will be determined based on the mean daily doses during the individual periods shown below.
 
Dose observation periods:
 
 At the start of treatment: Day 1 At Week 2: Day 2 to Day 14 At Week 4: Day 15 to Day 28 At Week 8: Day 29 to Day 56 At Week 16: Day 57 to Day 112 At Week 24: Day 113 to Day 168 At Week 32: Day 169 to Day 224 At Week 40: Day 225 to Day 280 At Week 48: Day 281 to Day 336 At Week 52: Day 337 to Day 364

No	Indicator of treatment status	Description
39	Maximum daily dose (safety) (mg/day)	
The maximum daily dose will be determined based on the maximum value of the daily dose during the duration of use of Lipacreon (safety). <900, 900, >900 and <1800, 1800, >1800, unknown/unspecified
 
In the summarization for the occurrence status of adverse events and adverse drug reactions, the maximum daily dose in a patient experiencing an adverse event or adverse drug reaction will be determined based on the maximum daily dose until the time of initial onset of the event.

40	Maximum daily dose (effectiveness rate) (mg/day)	
The maximum daily dose will be determined based on the maximum value of the daily dose during the duration of use of Lipacreon (effectiveness rate). <900, 900, >900 and <1800, 1800, >1800, unknown/unspecified

41	Last daily dose (safety) (mg/day)	
The last daily dose will be determined based on the last daily dose during the duration of use of Lipacreon (safety). <900, 900, >900 and <1800, 1800, >1800, unknown/unspecified
 
In the summarization for the occurrence status of adverse events and adverse drug reactions, the last daily dose in a patient experiencing an adverse event or adverse drug reaction will be determined based on the dose at the time of initial onset of the event.

42	Last daily dose (effectiveness rate) (mg/day)	
The last daily dose will be determined based on the last daily dose during the duration of use of Lipacreon (effectiveness rate). <900, 900, >900 and <1800, 1800, >1800, unknown/unspecified

3. Analysis Methods

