4.2. Summarization concerning Safety

4.2.1. Occurrence status of adverse events and adverse drug reactions

- Patients for summarization: Patients included in the safety analysis

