4.2.3.1. Incidence of adverse drug reactions by patient demographics

For patients included in the safety analysis, the number of patients, the percentage of patients, the number of patients with adverse drug reactions, the number of adverse drug reactions, and the percentage of patients with adverse drug reactions will be calculated for each of the demographic factors and indicators of treatment status defined in Section 2.3. In addition, for items that are unordered categorical variables, their independence from the incidence of adverse drug reactions will be tested using a Fisher's exact, and for items that are ordered variables (e.g., duration of treatment), their independence from the incidence of adverse drug reactions will be tested using a Kruskal-Wallis test to detect factors possibly affecting the incidence of adverse drug reactions (Table 2.3.1.1).

For demographic factors and indicators of treatment status that are found statistically significant in Table 2.3.1.1, lists of reported adverse drug reactions by category will be prepared (Table 2.3.1.2.X).

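### If the cut at first onset in SAP 2.3 item 24 applies in the adverse drug reaction factor table (Table 2.3.1.1), the duration test there is not valid; the SAP does not say whether it applies

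*SAP*

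**What the plan says.** **The cut.** SAP 2.3 item 24 (categorical treatment duration for safety) says that the duration of a patient with an event "will be determined based on the number of days until the initial onset date of the event (including the date of onset". Item 39 (maximum daily dose) has a matching rule: the value "will be determined based on the maximum daily dose until the time of initial onset of the event". Item 41 (last daily dose) takes the dose at first onset. A patient without an event is measured over the whole treatment period, which SAP 2.2 item 2 closes at 31 March 2018 if treatment is ongoing.

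**Its scope.** All three items limit the cut with the same words: "In the summarization for the occurrence status of adverse events and adverse drug reactions". No section or table number follows. The words resemble the heading of 4.2.1, "Occurrence status of adverse events and adverse drug reactions".

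**The factor table.** Section 4.2.3.1 builds Table 2.3.1.1, which gives ADR incidence "for each of the demographic factors and indicators of treatment status defined in Section 2.3". Its example of an ordered item is duration: "e.g., duration of treatment), their independence from the incidence of adverse drug reactions will be tested using a Kruskal-Wallis test". A significant row triggers a listing (Table 2.3.1.2.X). Section 3.2 sets a two-sided 5% level with no multiplicity adjustment.

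**Items without a cut.** Item 26 has the same name as item 24, "Duration of treatment (safety) (excluding any rest period", but is the actual value. Item 30 is "Actual value of the total dose during the duration of use of Lipacreen (safety". Item 28 (total dose in categories) has no cut either.

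**The concern.** In an ADR table with the cut applied, the duration of an ADR patient is the time to the ADR. The duration of every other patient is the time to the end of treatment. These are different quantities. ADR patients are moved into the shorter categories because they had the outcome, so a trend can appear when duration has no effect at all.

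The protocol (section 9(3)) lists factors that influence safety as an analysis item, and Table 2.3.1.1 is the only planned test of such factors for ADRs. A false signal that short treatment carries more ADRs, or its opposite, could enter the re-examination output together with an extra listing.

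**Working it through.** **Where the cut could act.** I compared the wording of items 24, 39 and 41 with each table:

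- Tables 2.1.2.1 to 2.1.2.4 use their own onset intervals, not the item 24 categories.
- Table 2.1.5.1 lists days of treatment, maximum dose and last dose per patient. It gives duration and dose at first ADR as separate items (20 and 22).
- The other 4.2.1 tables break events down by seriousness, causality, action taken, outcome or time to resolution.
- Table 2.3.1.1 uses all Section 2.3 items and tests them.

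So either the cut governs no categorical table, or it governs Table 2.3.1.1.

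**Inputs.** The documents give no sample size, ADR rate or discontinuation rate, so there is no figure of the plan to reproduce; the benchmark is the nominal 5%. From the documents: survey 30 August 2011 to 31 March 2018 (2,406 days), registration to 31 March 2017 (so at least 366 days of possible follow-up), the item 24 cut points, and national counts of 38 (ten years) and 13 (2004). Assumed: uniform entry, constant first-ADR hazard h (so duration has no effect), constant yearly discontinuation risk, and no stopping because of an ADR unless stated.

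**What the cut row measures.** Nobody reaches the survey end before day 366. A patient therefore falls in the bands up to 364 days only through an ADR or by stopping. With discontinuation hazard d, ADR incidence there is h/(h+d). At 10% per year, d = -ln(0.9) = 0.105:

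- h = 0.05: 0.05/0.155 = 32%
- h = 0.15: 0.15/0.255 = 59%
- d = 0: h/h = 100%, whatever h is

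The row thus reflects the ADR rate relative to the stopping rate, not an effect of duration. The same simulated patients (10% per year), banded both ways:

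| ADR incidence | ≤364 d | 365-1092 d | >1092 d |
|---|---|---|---|
| h = 0.05, cut | 32.2% | 13.5% | 7.4% |
| h = 0.05, uncut | 2.5% | 9.2% | 20.3% |
| h = 0.15, cut | 58.7% | 32.1% | 20.4% |
| h = 0.15, uncut | 7.1% | 24.9% | 49.2% |

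The trend reverses, although the true hazard is flat.

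**False rejection, item 24.** Kruskal-Wallis on duration category by ADR status, 20,000 simulated surveys per setting, ranges over h = 0.05 to 0.15:

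| Discontinuation per year | N = 38 | N = 13 |
|---|---|---|
| 0% | 55-82% | 17-33% |
| 10% | 23-41% | 6-14% |
| 20% | 11-18% | 3-8% |
| 30% | 6-10% | not run |
| 50% | 3-5% | not run |

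Repeat runs differ by a point or two, so I round the first two N = 38 figures to 55-80% and 25-40%. At h = 0.01 to 0.02 with 10% per year, rejection is about 4-10% at N = 38 and 0.5-2% at N = 13. If ADR status is instead compared across duration categories (the SAP does not say which way round), N = 38 gives 24-46%, 8-20% and 5-14% at 0, 10 and 20% per year.

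A second model isolates the cut: a 20% ADR share independent of whole duration, with onset uniform over treatment, N = 38. Rejection is 4.5% uncut and 57% cut.

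**Uncut duration.** At constant hazard and N = 38, rejection is 18-40% with no discontinuation and 22-54% at 10% per year, almost all toward longer duration, because longer treatment gives more time for an ADR. If every ADR patient stops at the ADR, it is 23-40% toward shorter duration (10% per year). Total dose with constant doses gives 10-40% and 14-54% at 0 and 10% per year.

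**Maximum daily dose, cut.** N = 24 and 38, random upward steps through five ordered categories, unrelated to ADRs (step rates assumed):

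| Steps per year | Uniform onset | Early onset |
|---|---|---|
| 0 | 4.6-6.0% | 4.7-4.9% |
| 0.1 | 3.9-5.7% | 4.6-7.5% |
| 0.25 | 5.3-6.7% | 9.9-18.9% |
| 0.5 | 10.0-17.9% | 22.8-48.6% |

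With no dose change, cut and uncut results are identical.

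**The case against.** **The cut may be confined to 4.2.1.** Its scope wording echoes that heading, and Table 2.3.1.1 would then be unaffected. This stands as a possibility. A reader might infer that the SAP definitely tests the cut duration; the text does not go that far. Since no 4.2.1 table uses the categories, it does not settle the matter the other way either.

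**Two contradictory duration tests.** A reader might infer that the SAP plans to test both item 24 and item 26. That is not established. Section 4.1.3.1 gives the actual values of duration and total dose a use as summary statistics in Table 1.3.1, and the counts and percentages in Table 2.3.1.1 suit categories. Categorical total dose (item 28) is clearly a row.

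**Which event cuts.** In an ADR table the event is naturally the ADR, and Table 2.1.5.1 already refers to first ADR onset. This stands; one confirming sentence is enough.

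**Other tables help.** The onset bands match the dose periods of Table 2.2.1 (Weeks 48 and 52 combined) and the discontinuation bands of Table 1.1.2, so rough denominators can be pieced together. In part this stands. But the percentages in Tables 2.1.2.1 to 2.1.2.4 divide by the whole safety set, and patients on a dose are not the same as patients at risk of a first ADR.

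**The dose cut has a purpose.** It avoids counting dose changes made because of the ADR. This stands, and a reader should not infer that the dose rows are invalid in general.

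**The size is assumed.** This stands: low hazards, few patients or heavy discontinuation leave little or no inflation.

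**Conclusion.** The concern holds in conditional form. If the item 24 cut acts in Table 2.3.1.1, the duration row is invalid by construction. How often it misleads depends on rates that the documents do not give. At N = 38 and constant hazards of 0.05 to 0.15 per year, false rejection is roughly 55-80% without discontinuation and 25-40% at 10% per year. It falls to about 4-10% at hazards of 0.01 to 0.02 with 10% per year, and to little or none with heavy discontinuation or with N = 13 and low hazards.

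Replacing the cut with whole duration, or relying on categorical total dose, does not repair the test. Maximum and last daily dose cover different time spans in patients with and without an ADR. They are distorted only if doses change, and slightly if changes are rare.

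A reader might infer that the safety conclusions are at risk. They are not: these are unadjusted exploratory tests, and the consequence is misleading factor signals and extra listings. Severity is minor to should-fix.

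**What to change.** 1. In SAP 2.3 and 4.2.3.1, name the tables to which the onset cut applies, and state that in ADR tables the event is the first ADR.
2. In Table 2.3.1.1, give no p-value for duration (item 24, and item 26 if tabulated there), total dose (item 28, and item 30 if tabulated), maximum daily dose (item 39) or last daily dose (item 41). Leave these rows descriptive. Keep the tests for factors fixed on Day 1, including initial daily dose.
3. For duration, report first ADRs per person-time at risk in a few intervals (for example ≤364, 365-1092 and >1092 days) with exact Poisson intervals. End person-time at first ADR, end of treatment or 31 March 2018, and exclude rest periods. List separately any ADR with onset after treatment ends or during a rest period. Rates by current dose category are optional.

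**Cost.** A few exploratory p-values are lost and one table is reprogrammed. No new data are needed, since onset dates and dated dose records are already collected.

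The rates will be imprecise. With h = 0.05, 10% per year, k = 0.05 + 0.105 = 0.155 and possible follow-up uniform from 1.00 to 6.59 years, the chance of a first ADR is (0.05/k) × {1 - [exp(-1.00k) - exp(-6.59k)]/(5.59k)} = 0.322 × (1 - 0.572) = 0.138. That is 38 × 0.138 = 5.2 first ADRs, or 13 × 0.138 = 1.8. In simulation at N = 38 the three intervals expect 1.8, 2.3 and 1.1, and the median 95% interval for the first-year rate is 0.7 to 19.9 per 100 person-years.

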8	Concomitant drugs (safety)	Among the drugs recorded in the “3. Status of Use of Concomitant Drugs” column, any drug that has a recorded duration of use, meets the condition (its start date of use is between the start date of treatment with Lipacreon and the end date of treatment with Lipacreon [safety]) (including its continued use at the time of the start of treatment with Lipacreon), and is used for reasons other than “treatment of any adverse event” will be deemed as a concomitant drug. (This is because it will not be possible to obtain correct results if any drug used to treat an adverse event is included when determining whether any difference in the incidence of adverse drug reactions exists between when any concomitant drug is used or not used)
9	Concomitant drugs (effectiveness rate)	Among the drugs recorded in the “3. Status of Use of Concomitant Drugs” column, any drug that has a recorded duration of use, meets the condition (its start date of use is between the start date of treatment with Lipacreon and the end date of treatment with Lipacreon [effectiveness rate]) (including its continued use at the time of the start of treatment with Lipacreon), and is used for reasons other than “treatment of any adverse event” will be deemed as a concomitant drug. (This is because it will not be possible to obtain correct results if any drug used to treat an adverse event is included when determining whether any difference in the incidence of adverse drug reactions exists between when any concomitant drug is used or not used)

No	Definition name	Description
10	Digestive enzyme preparations	Drugs corresponding to the following codes: Codes that begin with 2331 or 2339 *Excluding the code corresponding to Lipacreon
11	Adverse events	All events recorded in the “4. Adverse Event” column
12	Relationship with Lipacreon	The relationship with Lipacreon will be assessed as “Related” if the “causal relationship with Lipacreon” is “related,” “possibly related,” or “cannot be determined,” and as “Not related” if the “causal relationship with Lipacreon” is “unrelated.”
13	Adverse drug reactions	Among adverse events, any event whose “causal relationship with Lipacreon” is assessed as “Related” If the same adverse event (preferred term [PT]) occurs repeatedly and is recorded multiple times, any event related with Lipacreon will be counted.

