3.2. Testing

When any test is applied, a two-sided level of significance of 5% will be used without correction for continuity or adjustment of multiplicity.

P-values will be displayed with two asterisks (**) when being larger than 0 (zero) and less than 0.01 and with one asterisk (*) when being greater than or equal to 0.01 and less than 0.05. For any unknown/unspecified value, its frequency will be displayed in the tabulation, but it will not be included in the calculation for testing.

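### The ADR factor tests in SAP 4.2.3.1 include items that can follow from the reaction: reason for dose change (No. 32) and digestive enzymes started after onset (No. 22)

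*SAP*

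**What the plan says.** SAP 4.2.3.1 states that patient counts and ADR incidence "will be calculated for each of the demographic factors and indicators of treatment status defined in Section 2.3". It then applies Fisher's exact test to unordered items and the Kruskal-Wallis test to ordered ones, "to detect factors possibly affecting the incidence of adverse drug reactions" (Table 2.3.1.1). No item is exempted. Items found significant get a further listing of ADRs by category (Table 2.3.1.2.X). Under SAP 3.2, "a two-sided level of significance of 5% will be used without correction for continuity or adjustment of multiplicity".

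Two Section 2.3 items matter here:

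- **No. 32, reason for dose change (safety).** It covers the whole duration of use, allows several answers, and begins its categories with "Unsatisfactory therapeutic effect, occurrence of an adverse event".
- **No. 22, "Presence or absence of concomitant digestive enzyme preparations".** Read with SAP 2.2 No. 8, a drug is concomitant if it was in use when Lipacreon started or was begun at any time up to the end of Lipacreon treatment (safety definition). Drugs used to treat an adverse event are left out.

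The SAP does address reverse causation elsewhere. No. 8 gives its reason: "it will not be possible to obtain correct results if any drug used to treat an adverse event is included". For patients with an event, duration of treatment (No. 24) "will be determined based on the number of days until the initial onset date of the event", and maximum and last daily dose (Nos. 39 and 41) are likewise taken up to or at first onset.

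**The concern.** A test meant to find what affects ADR incidence should use items whose value could not have been changed by the ADR. No. 32 fails this directly, because a dose change made for an adverse event comes after the event. No. 22 can fail it too, if an enzyme is added after the reaction for a reason not recorded as treating it.

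Either item could then receive a significance asterisk in Table 2.3.1.1 and its own Table 2.3.1.2.X, both of which are re-examination outputs. A consequence of the reaction would be presented as a factor that may affect it. Because the SAP applies the principle to Nos. 8, 24, 39 and 41, leaving out Nos. 22 and 32 is an inconsistency within the plan.

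**Working it through.** **Which exposure items are protected**

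| Section 2.3 item (safety) | Protection against post-onset change |
|---|---|
| No. 24 duration; No. 39 maximum dose; No. 41 last dose | Taken up to or at first onset in patients with an event |
| No. 22 digestive enzymes | Partial: drugs treating an event are excluded; no onset cut |
| No. 32 reason for dose change | None |
| Nos. 28/30 total dose; No. 34 compliance; No. 37 mean daily dose | None |

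For No. 22, Protocol section 8(4) lists reason for use only among the other concomitant drugs. For other digestive enzyme products it lists presence, name, daily dose and period. The case report form is not among the documents, so whether the No. 8 exclusion can be applied to enzymes cannot be settled here.

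**Inputs for the illustration.** The plan gives no sample size, ADR rate or dose-change rate, so there is no stated figure to reproduce. I take 38 patients, the ten-year count of CF patients in Protocol section 2. The number with ADRs (4) is an assumption. No. 32 has no level for patients whose dose did not change, so I also assume a yes/no variable for the adverse-event reason.

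**Formula.** With N patients, A of them with ADRs, and k patients giving the reason, the probability that x of the k are ADR patients is C(A,x)·C(N−A,k−x)/C(N,k). The two-sided Fisher p sums all tables no more probable than the one observed.

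*All 38 patients in the denominator, no non-ADR patient giving the reason:*
- 1 of 4: 4/38 = 0.105
- 2 of 4: 6/703 = 0.009
- 3 of 4: 4/8436 = 0.0005

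*2 of 4 ADR patients, plus some of the 34 others (an unrelated adverse event):*
- 1 other: (6·34 + 4)/8436 = 208/8436 = 0.025
- 2 others: (6·561 + 4·34 + 1)/73815 = 3503/73815 = 0.047

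*Only patients whose dose changed in the denominator (assume 10, including the 4 with ADRs):*
- 2 of 4: 6/45 = 0.133
- 3 of 4: 4/120 = 0.033

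*Smaller surveys, all patients in the denominator:*
- 20 patients, 3 with ADRs: 3/20 = 0.15, 3/190 = 0.016 and 1/1140 = 0.0009 for 1, 2 and 3 of 3
- 13 patients, 1 with an ADR: at most 1/13 = 0.077, so never significant

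**No. 22.** Assume 38 patients, 20% enzyme use before onset in both groups, and a share s of the remaining ADR patients starting an enzyme after onset that is not recorded as treatment of an event. The ADR group's rate becomes 0.2 + 0.8s. Exact enumeration of the Fisher test at p < 0.05, with 4 to 11 ADR patients, gives:

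| s | Chance of a significant result |
|---|---|
| 0 (pre-onset use only) | 2% to 3% |
| 20% | 10% to 16% |
| 40% | 25% to 44% |
| 60% | 47% to 77% |

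The documents give no value for s.

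**The case against.** The case against has four parts.

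1. **The SAP already handles the problem.** It does in part: the exclusion in No. 8 and the onset cuts in Nos. 24, 39 and 41 are real. A reader might infer that the No. 8 exclusion is the only safeguard, and the text does not support that. But none of these provisions reaches No. 32, and No. 22 is reached only in part.
2. **The association is not automatic.** A reader might infer that No. 32 is tied to ADRs strictly by construction. It is not: the category refers to any adverse event, whereas an ADR is one not judged unrelated, so a patient without an ADR can give this reason. That weakens the link without removing it, as the results of 0.025 and 0.047 show.
3. **The test may not be definable.** No. 32 allows several answers and has no level for an unchanged dose, so no single Fisher table follows from the SAP, and the choice of denominator moves p from 0.009 to 0.133. This stands, and it is a further reason not to test the item.
4. **Little depends on the result.** These are unadjusted screening tests, and the stated consequence is an extra listing. Tables 2.1.5.1 and 5.2.1.1 give onset dates, doses with dates and concomitant enzymes, so in a small survey much of the sequence can be checked by patient. This stands and limits the seriousness. It does not justify running a test whose result cannot be read as intended.

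**Conclusion.** The point holds as an inconsistency in an exploratory analysis, more strongly for No. 32 than for No. 22. Under the assumptions above, two of four ADR patients changing dose for the event are enough for significance when all 38 patients form the denominator, even if one or two others did the same. One of four is not enough, nor are two of four among ten dose-changers.

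A reader might infer that these items will appear as the strongest factors in Table 2.3.1.1. The documents do not support that, because they give no patient number, ADR count or dose-change rate, and the plausible results fall on both sides of 5%. What can be said is that the items can be flagged without affecting ADR risk. No confirmatory conclusion depends on them, but the correction should be made before the re-examination tables are produced.

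**What to change.** Three changes to the wording of SAP 4.2.3.1:

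1. Report No. 32 descriptively, with no test, and exclude it from the trigger for Table 2.3.1.2.X.
2. For the test of No. 22, classify every patient by digestive enzyme use on Day 1 of Lipacreon. Protocol section 8(4) already collects administration periods, so no new data are needed. Day 1 status has the same definition for everyone; an onset cut applied only to ADR patients would give them a shorter exposure window than the rest.
3. Label the results for total dose (Nos. 28/30), compliance (No. 34) and mean daily dose (No. 37) as possibly reflecting changes made after the reaction, since these items have no onset cut.

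The cost is that enzyme exposure begun after Day 1 but before onset no longer forms part of the tested factor. Enzymes started later stay in the patient listings.
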